## DATA AND SPECIMEN BANKING

NA

## SHARING RESULTS WITH PARTICIPANTS

Results will not be shared with participants or their medical providers.

## STUDY TIMELINES

- IRB submission and approval process: 2 months
- Recruitment: 12 months
- Statistical analysis and manuscript: 2 months
- Duration of participation for each participant is approximately: 3 weeks

## INCLUSION AND EXCLUSION CRITERIA

### INCLUSION CRITERIA

1. Age greater than 18 years of age at day of enrollment
2. Lower extremity amputation performed more than 12 months before study enrollment
3. PLP/RLP in affected amputated limb > 4 on NRS26
4. Pain duration of more than 6 months despite a trial of conservative therapies for at least 2 months, including oral medications, topical medicines, physical therapy, and physical modalities (i.e., heat, cold, transcutaneous electrical nerve stimulation, phonophoresis)
5. Willingness to undergo image guided diagnostic nerve block

### EXCLUSION CRITERIA

1. Refusal / inability to participate or provide consent
2. Contraindications to diagnostic nerve block
3. Non-neurogenic source of PLP/RLP
4. Current opioid use > 50 morphine milligram equivalents per day
5. Any interventional pain treatment in the residual limb within the last 30 days
6. Severe uncontrolled medical condition (i.e., hypertensive crisis, decompensated hypothyroidism)
7. Use of investigational pain drug within past 30 days or other concurrent clinical trial enrollment

## VULNERABLE POPULATIONS

NA

## PARTICIPANT POPULATION(S)

Accrual Number:	Category/Group: (Adults/Children Special/Vulnerable Populations)	Consented: Maximum Number to be Consented or Reviewed/Collected/Screened	Enrolled: Number to Complete the Study or Needed to Address the Research Question
Total:	1 Adult Group	20	20

STU#:

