### *Visit 1 – Consent, inclusion screening, and prosthetic step counter placement*

All participants will present to the Pain Clinic ([name]) and undergo an informed consent process with authorized research personnel. Eligibility criteria will be reviewed and confirmed. [name] will meet with the participant, explain the treatment block procedure, will review the medical history and perform a brief physical examination (focusing on residual limb point of maximal tenderness, review of prior imaging studies if available, and lower extremity musculoskeletal examination). Participants will provide baseline outcome measures and demographic data. Participants will be asked to complete the OPUS and GARS survey and provide demographic information. They will be given the option of completing these either on paper or on an iPad.

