Treatment block of sciatic nerve in contralateral limb: Procedure planning will be based on the participant’s indication of residual limb point of maximal pain (measured by distance from posterior superior iliac spine (PSIS) to most painful point [in cm]). Note that this point may beyond the anatomic end of the residual limb. The block will be performed at the exact same distance from PSIS on the contralateral side. If the block cannot be performed at this site due to anatomic or technical considerations (such as proximity to vascular structures), a more cephalad site along the sciatic nerve course will be selected for the procedure. During the block procedure, the participant will be positioned prone. Standard American Society of Anesthesiologists (ASA) procedure monitoring will be used (pulse oximetry, ECG, blood pressure, and heart rate). The participant’s skin will be prepared with chlorhexidine. A sterile ultrasound probe will be placed on the participants’ residual limb at a transverse angle in order to view the nerve in short-axis. The skin will be anesthetized with 1-2 mL of 1.0% lidocaine. The ultrasound probe (in plane) will be advanced to the intact limb’s sciatic nerve equidistance to that of the residual limb point of maximal pain. A 22-gauge standard echogenic needle will be placed adjacent to the sciatic nerve with ultrasound guidance. At the site of the nerve, 10mL of 2% lidocaine will be injected through the needle in the intervention group and 10ml of saline will be injected in the sham group.

In treatment group: At the site of the nerve, 10mL of 2% lidocaine will be injected through the needle

In control group: At the site of the nerve, 10ml of saline will be injected through the needle

Following injection, participants will be kept in recovery area and monitored for 30 minutes. They will also complete a pain log starting 15 minutes post-injection. After the first pain score is recorded, the participants will dress and exit procedure area. Participants will be required to arrange transportation as the block may impair lower extremity motor function.

Both saline and local anesthetic will be administered to all subjects with a crossover design as described above. Participants will undergo 5-day washout between injections.

*Visit 3 – Crossover for both groups*

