## POWER ANALYSIS

Power and sample size calculations for this clinical trial were performed based on the data from a small cross-over study (N = 8) by Casale et al. The primary outcome variable will be achievability of  $\geq 50\%$  pain relief (dichotomous variable with yes/no), calculated from pre- and post-inject NRS in each of the lidocaine and sham conditions (i.e., pre-injection NRS – post-injection NRS). Based on the data from Casale et al., along with our expected, overall success rate of 75% by lidocaine injection, we calculated the difference in two proportions of discordant pairs to be 0.625 and the overall proportion of discordant pairs to be 0.875. Using these values and binomial enumeration (1,500 enumerations), along with an

STU#:

alpha level of 0.05, a power of 0.80, a two-sided t-test, and a dropout rate of 10%, the sample size was estimated as 20.

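### The accrual table gives 20 as both the consent cap and the number to complete or needed, although the 20 in the power section already includes 10% dropout (minor)

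*Combined protocol and SAP*

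**What the plan says.** The accrual table under Participant Population(s) has one row, a single adult group, and two counts. The first is the maximum to be consented, reviewed or screened: 20. The second is headed as enrolled and defined as the "Number to Complete the Study or Needed to Address the Research Question": also 20.

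The Power Analysis reaches 20 with attrition included: "alpha level of 0.05, a power of 0.80, a two-sided t-test, and a dropout rate of 10%, the sample size was estimated as 20". Its effect inputs are "we calculated the difference in two proportions of discordant pairs to be 0.625" and "the overall proportion of discordant pairs to be 0.875". It does not print the evaluable number before inflation. The Study Summary and the Methods text also give 20, as sample size and as the number to be recruited.

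The order of events matters here. Candidates are first screened by chart review (Methods, pre-visit). At Visit 1 they consent, and then "Eligibility criteria will be reviewed and confirmed". Randomisation is at Visit 2, up to two weeks later. The withdrawal section lets participants leave at any time and lets the team remove those who do not comply. The documents contain no replacement rule and no allowance for losses between consent and randomisation.

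**The concern.** Three different quantities carry the same value: the number who may consent, the number randomised, and the number who complete or are needed. A 10% dropout allowance makes sense only if the completers are fewer than the randomised. When consent precedes the eligibility check, the number consented normally has to exceed the number randomised.

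Two things are at stake. First, the table misreports what the research question needs, because the power calculation does not call for 20 completers. Second, each person who consents and then fails the eligibility check, or leaves before Visit 2, uses one of the 20 consent places. Under the cap the trial then randomises fewer than 20 and cannot replace the loss without an amendment.

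**Working it through.** **Inputs (Power Analysis).** Difference between the two discordant proportions 0.625; total discordant proportion 0.875; two-sided alpha 0.05; power 0.80; dropout 10%. Solving p10 + p01 = 0.875 and p10 − p01 = 0.625 gives p10 = 0.75 and p01 = 0.125.

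**Method assumed.** The plan says "Using these values and binomial enumeration (1,500 enumerations") but names no paired test. Every participant receives both injections, so the exact two-sided McNemar (binomial) test is the natural candidate. Its power at n pairs is the sum over m of P(M = m) × P(reject | m). Here M, the number of discordant pairs, is Binomial(n, 0.875). Given m, the count favouring lidocaine is Binomial(m, 0.75/0.875).

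**Reproducing the plan's 20.**

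| Completers | Exact power |
|---|---|
| 16 | 0.748 |
| 17 | 0.790 |
| 18 | 0.830 |
| 19 | 0.859 |
| 20 | 0.879 |

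The smallest n with power of at least 0.80 is 18, and 18/0.9 = 20. This matches the plan. Other variants do not match exactly: uncorrected McNemar by enumeration needs 16 pairs (18 with dropout), and the continuity-corrected version needs 19 (22 with dropout).

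**Reading 1: the second 20 is a completer count.** With 20 randomised and 10% dropout, expected completers are 20 × 0.9 = 18. The chance that all 20 complete is 0.9^20 = 0.12. To expect 20 completers, 20/0.9 = 22.2, so 23 would have to be randomised, which is above the cap.

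**Reading 2: the second 20 is the number enrolled.** It then equals the consent cap. Averaging exact power over completers distributed as Binomial(N randomised, 0.9):

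| Lost before randomisation | Randomised | Expected completers | Average power |
|---|---|---|---|
| 0 | 20 | 18.0 | 0.823 |
| 1 | 19 | 17.1 | 0.792 |
| 2 | 18 | 16.2 | 0.758 |

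The documents give no rate of loss between consent and randomisation. For assumed rates s, with 20 consented and completers distributed as Binomial(20, 0.9 × (1 − s)):

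| Assumed s | Expected completers | Average power | Consents needed to randomise 20, 20/(1 − s) |
|---|---|---|---|
| 3% | 17.5 | 0.804 | 20.6, so 21 |
| 5% | 17.1 | 0.791 | 21.05, so 22 |
| 10% | 16.2 | 0.758 | 22.2, so 23 |

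**The case against.** The table's second heading offers alternatives and is introduced as enrolled. The other places that give 20 (Study Summary, Methods, Power Analysis) are sample-size or recruitment figures, and none is a completer requirement. On that reading the cell agrees with the Power Analysis. This stands: the table is ambiguous and not flatly impossible. It does not clear the table, because an enrolment target equal to the consent cap still leaves no place for a pre-randomisation loss.

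Chart review before Visit 1 should keep such losses low, and the eligibility step at Visit 1 is a second check. This also stands, and the assumed rates above have no source in the documents. Even so, some criteria, such as a pain score above 4 and willingness to have the block, are hard to settle from a chart, and up to two weeks separate consent from randomisation.

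A reader might infer that the trial cannot reliably reach its stated power. The documents do not support that. The allowance inside the 20 is what protects the power: if all 20 are randomised and 10% drop out, average power is 0.82. The chance of at least 18 completers is then 68%, but that comes from inflating by the expected dropout. It would be the same under any consent cap that still yields 20 randomised. Likewise, the 12% chance of 20 completers says nothing about power, since the calculation needs 18.

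Finally, 18 is inferred and not printed, and it depends on the test.

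**Conclusion.** The table is wrong as written, at minor severity. As a completer count, 20 of at most 20 consented is incompatible with the plan's 10% dropout. As an enrolment figure, it leaves no margin between consent and randomisation. The consequence for power is modest: 0.82 on average with no pre-randomisation loss, about 0.79 with one and 0.76 with two, against a stated 0.80. Calling the trial underpowered on this ground would go beyond the documents.

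The figures rest on three assumptions: an exact two-sided McNemar test; the plan's discordance inputs taken at face value; and the 10% dropout counted from randomisation, which the plan does not specify. They do not describe the unpaired tests in the Statistical Plan, which are a separate matter.

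**What to change.** In the Participant Population(s) table, state 20 randomised and 18 evaluable completers needed. Set the consent maximum as its own figure above 20, with the assumed pre-randomisation loss stated beside it: for example 22 at 5% or 23 at 10%. Print the 18 in the Power Analysis, name the test behind it, and say from which point the 10% dropout is counted. State whether participants lost before randomisation may be replaced.

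If the cap must stay at 20 consented, give the completers then expected and the power that goes with them. If 20 completers are truly wanted, the number randomised would have to rise to 23, but the power calculation does not require this.

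The cost is an IRB amendment centred on one table, with the matching clarification in the power text, and a few more consents. The number randomised stays at 20, and the design and analysis are unaffected.

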## **RECRUITMENT METHODS**

Participants will be recruited from the Northwestern-affiliated practices of the PI, the Shirley Ryan Ability Lab, the University of Chicago, and local prosthetic clinics. The trial will be posted on clinicaltrials.gov. IRB approved flyers will also be used.

## **COMPENSATION FOR PARTICIPATION IN RESEARCH ACTIVITIES**

None

## **WITHDRAWAL OF PARTICIPANTS**

Participants may withdraw from the study at any time. Participants may be withdrawn from the research without their consent if they are non-compliant with providing outcome measures or study visits.

## **RISKS TO PARTICIPANTS**

Ultrasound-guided perineural anesthetic injection is a commonly performed procedure in the U.S. and is considered safe and effective in treating chronic pain. It is considered very safe when performed with image guidance and by an experienced injectionist. The major complication (permeant nerve injury) rate following peripheral nerve block is estimated to be 1.5 / 10,000^42.

### **RISKS RELATED TO NEEDLE PLACEMENT**

- Temporary bruising or swelling at the site of the injection
- Hematoma (pocket of blood caused by bleeding from a broken blood vessel)
- Infection of the tissues of the leg surrounding the area of injection

### **RISKS RELATED TO INJECTION OF MEDICATIONS**

#### **Lidocaine Risks**

Infrequent

- Bradycardia
- Hypotension
- Drowsiness
- Dizziness
- Muscle twitching
- Nervousness
- Paresthesia
- Sensation of feeling cold
- Anxiousness

Rare

- Allergic reaction to lidocaine
- Skin injury including ulceration at the site of the injection
- Methemoglobinemia
- Diplopia
- Cardiac manifestations: Bradycardia, tachycardia, ventricular tachycardia, ventricular fibrillation, asystole, wide / premature QRS, bundle branch block, II to III AV block, ST changes, ventricular ectopy
- Respiratory depression
- Unconsciousness

STU#:

- Seizure
- Nausea
- Apprehension

Normal Saline Risks

- Hypernatremia

Loss of confidentiality

## **POTENTIAL BENEFITS TO PARTICIPANTS**

Individual participants may experience short- or long-term improvements in pain as a result of participation in this research.

## **DATA MANAGEMENT AND CONFIDENTIALITY**

All data will be de-identified and recorded in duplicate on electronic study-specific case report forms (CRFs). Data will be entered utilizing REDCap. Participants will be given a study identification number that will be reported on all CRFs and source documents. Only the PI and authorized staff, according to the list of Authorized Study Personnel, are entitled to make entries on the CRF. Personal participant data will be kept confidential. Participant documentation will identify a participant by initials and study number. Only the PI will keep in his file a Participant Identification and Enrollment List. To allow compliance with GCP principles, each participant will be asked for consent regarding the access to source documents for monitoring, audits, and inspections. Data both electronic and paper will be destroyed 5 years after manuscript completion using current vendors and department protocol. Paper documents will be stored in the Arkes 10th floor Anesthesiology Administrative Office which is key card controlled in a locked research closet.

## **PROVISIONS TO MONITOR THE DATA TO ENSURE THE SAFETY OF PARTICIPANTS**

A data safety monitoring board consisting of the Department of Anesthesiology Director of Research, a pain medicine attending physician, a statistician, and study research personnel will periodically evaluate the data collected to determine whether participants remain safe. Safety data and adverse event data will be reviewed using the medical record and data collection form. It will be reviewed every 10 subjects or if one of the study subjects experiences a rapid response team intervention. Data will be compared between groups using the  $\chi^2$  statistic or the Fisher's exact test. A p-value  $< 0.05$  will be required to reject the null hypothesis.

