**PROCEDURES INVOLVED:**

Study Design

We aim to conduct a single-site, prospective, randomized, triple blind, sham-controlled, cross-over trial of consecutive participants to determine the efficacy of contralateral sciatic nerve block in treating chronic, refractory PLP/RLP.

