### *Visit 2 (procedure 1)– Randomization and Study Intervention*

STU#:

Eligible participants will return to the Lavin 14th floor Pain clinic within 2 weeks of the initial visit. Participants will be randomized to treatment or sham group. Participant pre-procedure 1 NRS pain score will be collected. Individual pain log will start 15 minutes after procedure. Participant will log pain score every hour until asleep. The next day, participant will record daily NRS pain score for 5 days.

Randomization

A computer-generated 1:1 block randomization scheme (<https://www.randomizer.org>) will be used to assign participants to receive a peri-sciatic nerve injection with either 10 mL of 2% lidocaine or 10 mL of preservative-free saline (compounded by the 11th floor Lavin pharmacy and labeled with a “1” or “2” to ensure adequate blinding). Randomization will be performed by a research assistant by opening an opaque envelope to reveal the participant number and group assignment printed inside of the envelope. This will instruct authorized study personnel to draw up either 2% lidocaine or saline (labeled “1” or “2” by compounding pharmacy per above). The blinded injectionist will be provided an unlabeled syringe of injectate immediately before the injection procedure. Participants, injectionist, and study personnel who collect outcomes data will be blinded to group assignment.

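### Nothing separates the study staff on the safety board, which compares groups after every 10 of 20 subjects, from the staff who must stay blinded

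*Combined protocol and SAP*

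**What the plan says.** The Study Design paragraph describes a "randomized, triple blind, sham-controlled, cross-over trial of consecutive participants". The Randomization text under Visit 2 says who is blinded: "Participants, injectionist, and study personnel who collect outcomes data will be blinded to group assignment". The pharmacy's injectates are "labeled with a “1” or “2” to ensure adequate blinding". A research assistant opens an envelope that shows the group assignment, other authorized personnel draw up the injectate, and the injectionist receives an unlabeled syringe.

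The section on provisions to monitor the data for participant safety creates a board made up of the department's Director of Research, a pain physician, "a statistician, and study research personnel will periodically evaluate the data collected". On timing it says: "It will be reviewed every 10 subjects or if one of the study subjects experiences a rapid response team intervention". On method it says "Data will be compared between groups using the" chi-square or Fisher exact test, at p < 0.05. The Study Summary, however, answers No on the line for DSMB / DMC / IDMC.

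**The concern.** A board that looks at data by group has to be kept apart from the people whose ignorance of allocation protects the trial. Here the board's membership includes staff of the trial itself. The protocol does not say which staff, does not provide a separate closed report, and does not say that the group labels are masked for the board.

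The primary endpoint is the proportion with at least 50% improvement in NRS from baseline at 15 minutes. It is a subjective score, and it depends on the pre-procedure score as well as the later one. Staff who hold or suspect the key to the labels before an injection could affect how either score is given, without meaning to. The trial's conclusion rests on the lidocaine and saline conditions being handled alike.

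**Working it through.** **1. The denominator.** The Power Analysis section gives the inputs: "we calculated the difference in two proportions of discordant pairs to be 0.625 and the overall proportion of discordant pairs to be 0.875". It also gives two-sided alpha 0.05, power 0.80 and 10% dropout.

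- Discordant probabilities: (0.875 + 0.625)/2 = 0.75 and (0.875 − 0.625)/2 = 0.125.
- Exact two-sided McNemar power, summed over the number of discordant pairs m ~ Bin(n, 0.875), with the favourable pairs among them ~ Bin(m, 0.75/0.875 = 0.857): n = 17 gives 0.790 and n = 18 gives 0.830.
- Smallest n reaching 0.80 is 18. Allowing for dropout, 18/(1 − 0.10) = 20.

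The planned 20 is reproduced.

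**2. What remains after the first scheduled look.** I count the first 10 subjects as having had both injections. The text does not say whether subjects are counted at enrolment or at completion.

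- Participants still to come: 20 − 10 = 10, and 10/20 = 50%.
- Injections still to come: 2 × 10 = 20 of 2 × 20 = 40.
- On 18 completers: 18 − 10 = 8, and 8/18 = 44%.
- A rapid response event could bring a by-group review earlier.

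**3. The roles, side by side.**

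| Role | Blinded under the protocol? | Could sit on the board? |
|---|---|---|
| Injectionist | Yes | Not excluded |
| Staff who collect outcomes | Yes | Not excluded |
| Staff who open envelopes or draw up injectate | Not listed as blinded | Not excluded |
| Director of Research, pain physician, statistician | Not stated | Named as members; other trial roles not stated |

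**4. The steps from the board to the primary outcome.** Each of these would have to happen.

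- *A board member also has a blinded role.* The text neither says so nor rules it out.
- *The table gives away the label.* The procedure text warns that the block may weaken the leg, and the risk list for lidocaine includes paresthesia. A table by injectate with such events under one label would be informative. Because everyone receives both injections, the groups could also mean the two sequences; the text does not say.
- *The label keeps its meaning.* Two labels for the whole trial is the natural reading of the Randomization text, but it is not stated.
- *The person learns a later participant's label.* Summaries of the first 10 do not show this. The staff who open envelopes and draw up injectate do see assignments, so a route exists within the team. In a two-period crossover, knowing one period gives the other.
- *That knowledge affects a score.* Pre-procedure NRS is collected at each procedure visit, and a research coordinator telephones for later NRS and OPUS. The 15-minute score is entered in the participant's own log, in the recovery area.

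The documents establish none of these steps, and they contain no safeguard that blocks the chain.

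**The case against.** The strongest reply is that the two sections do not contradict each other. Only participants, the injectionist and outcome collectors are promised blinding, and the protocol already has staff who handle allocation. The study personnel on the board could be those people. The review also concerns safety and adverse event data, the injectionist's syringe is unlabeled, and leg weakness or numbness may reveal lidocaine at the bedside whatever the board does.

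Much of this stands, and it rules out several stronger readings that a reader might infer:

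- *That the blind will be broken.* The documents show only that it is not protected at this point.
- *That staff will see interim efficacy results.* The section describes safety data, not a by-group look at the primary outcome.
- *That staff record the 15-minute score.* The procedure and device text describe a log kept by the participant.
- *That 20 of 40 injections would be biased.* That is a count of what follows the first scheduled look, not an estimate of damage.
- *That no new board members could be needed.* This depends on the three named members having no role in recruitment, injection or outcome collection, which is not stated.

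Two parts of the reply do not dispose of the point. That the board's staff could be people outside the blind is a possibility, not a rule in the protocol. And bedside signs appear only after the injection, whereas knowledge of the label could exist beforehand and so touch the pre-procedure score too.

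**Conclusion.** The concern holds in a limited form. The monitoring section gives undefined study personnel a seat where safety data are compared by group, and nothing separates them from the injectionist and outcome collectors who are meant to be blinded. Blinded staff could therefore be exposed to by-group safety data, and possibly to the meaning of the labels, with up to 10 of 20 participants (50%), or 8 of 18 completers (44%), still to be treated after the first scheduled look.

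These fractions rest on a count of subjects who have had both injections and on no earlier event-driven review. Any effect on the primary comparison depends on the further steps listed above and cannot be sized from the documents. I rate this as a cheap improvement worth making, with moderate confidence.

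**What to change.** Reword the monitoring section to say four things:

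- Study personnel who recruit, inject or collect outcomes supply data to the board and see pooled results only.
- By-group tables go only to board members confirmed in writing to have no such role: for example the statistician, and the Director of Research and the pain physician if they have none.
- Those tables carry masked group labels that differ from the pharmacy's 1 and 2.
- The groups being compared are defined (injectate or sequence), and so is the point at which a subject counts toward the 10.

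Correct the Study Summary or the monitoring section so that they agree on whether a board exists.

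The review schedule and its trigger need not change. The cost is a few sentences, plus a replacement member if one of the three named proves to have a conflicting role. The downside is that study staff will not see by-group safety tables during the trial. Rewording will not remove unblinding by sensory or motor signs at the bedside, which is a separate matter.
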